## 6.2. Exclusion Criteria

Subjects will be excluded from study enrollment if they meet any of the following criteria at screening and/or Day -1:

- [9] are site staff directly affiliated with this study and their immediate families.  
Immediate family is defined as a spouse, biological or legal guardian, child, or sibling
- [10] are Lilly employees or are employees of a third-party organization involved in the study
- [11] are currently enrolled in a clinical study involving an IP or any other type of medical research judged not to be scientifically or medically compatible with this study
- [12] have participated in a clinical trial involving an IP within 30 days or 5 half-lives (whichever is longer) prior to screening. If the clinical trial involved treatment with biologic agents (such as monoclonal antibodies, including marketed drugs), at least 3 months or 5 half-lives (whichever is longer) should have elapsed prior to Day 1
- [13] have previously completed or withdrawn from this study or any other study investigating mirikizumab, and have previously received the IP
- [14] have ever received anti-IL-12p40 antibodies (eg, ustekinumab [Stelara®]) or anti-IL-23p19 antibodies (eg, risankizumab [BI-655066], brazikumab [MEDI2070], guselkumab [CNTO 1959], or tildrakizumab [MK-3222]) for any indication, including investigational use
- [15] have known allergies to mirikizumab, related compounds, or any components of the formulation, or history of significant atopy
- [16] have self-perceived dullness or loss of sensation in either arm or thigh or on either side of the abdomen
- [17] have an abnormality in the 12-lead ECG that, in the opinion of the investigator, increases the risks associated with participating in the study
- [18] have an abnormal blood pressure, pulse rate, or temperature as determined to be clinically significant by the investigator
- [19] have a history or presence of cardiovascular, respiratory, hepatic, renal, gastrointestinal, endocrine, hematological, or neurological disorders capable of significantly altering the absorption, metabolism, or elimination of drugs; of constituting a risk when taking the IP; or of interfering with the interpretation of data

[20] Infections:

- [20a] have had a serious infection (eg, pneumonia, cellulitis, sepsis); have been hospitalized or have received IV antibiotics for an infection within 12 weeks prior to Day 1; have had a serious bone or joint infection within 24 weeks prior to Day 1 or have ever had an infection of an artificial joint; or are immunocompromised to an extent that participation in the study would pose an unacceptable risk to the subject as determined by the investigator
- [20b] have or have had an infection typical of an immunocompromised host and/or that occurs with increased incidence in an immunocompromised host (including, but not limited to, *Pneumocystis jirovecii* pneumonia, histoplasmosis, or coccidioidomycosis) or have a known immunodeficiency
- [20c] have or have had a herpes zoster infection or any other clinically apparent varicella-zoster virus infection within 12 weeks of Day 1
- [20d] have had any other active or recent infection within 4 weeks of Day 1 that, in the opinion of the investigator, would pose an unacceptable risk to the subject if participating in the study; these subjects may be re-screened (once)  $\geq 4$  weeks after documented resolution of symptoms

- [21] have known or ongoing psychiatric disorders deemed clinically significant by the investigator
- [22] regularly use known drugs of abuse and/or show positive findings on drug screening
- [23] show positive HIV antibodies
- [24] show positive hepatitis C antibody
- [25] show positive hepatitis B surface antigen or hepatitis B core antibody
- [26] are women who are lactating
- [27] intend or are likely to use over-the-counter or prescription medication for pain or inflammation within 7 days prior to dose administration. Subjects on stable doses of other medications (eg, statins and antihypertensives) may be eligible for enrolment following discussion with the sponsor (Section 7.7)
- [28] have donated blood or plasma of more than 500 mL within 1 month prior to screening
- [29] have an average weekly alcohol intake that exceeds 21 units per week (males) and 14 units per week (females), have a positive test for ethanol, or are unwilling to abide by the alcohol restrictions described in Section 6.3.2 of 3 units per day (males) or 2 units per day (females) (1 unit = 12 oz or 360 mL of beer; 5 oz or 150 mL of wine; 1.5 oz or 45 mL of distilled spirits)

- [30] have a tobacco consumption of more than 10 cigarettes per day (or equivalent), or who are unwilling to abide by the CRU smoking guidelines described in Section 6.3.2
- [31] show evidence of active or latent TB, as documented through medical history, examination, and TB testing (positive [not indeterminate] QuantiFERON®-TB Gold test; if a repeat test is also indeterminate, the subject will not be eligible); or have had household contact with a person with active TB, unless appropriate and documented prophylaxis treatment has been given. Subjects with any history of active TB are excluded from the study, regardless of previous or current TB treatments
- [32] have received live vaccine(s), including attenuated live vaccines and those administered intranasally, within 8 weeks of screening, or intend to during the study (non-live or inactivated vaccinations are not allowed 2 weeks prior to, or 2 weeks after mirikizumab dosing, and then they must be given at an injection site remote from mirikizumab administration)
- [33] have been treated with oral steroids within 1 month of screening, or intend to during the study (mild topical steroid creams/ointments are permitted, with the exception of the injection day as specified in Section 7.7)
- [34] have significant allergies to humanized monoclonal antibodies
- [35] have clinically significant multiple or severe drug allergies, or intolerance to topical corticosteroids, or severe posttreatment hypersensitivity reactions (including, but not limited to, erythema multiforme major, linear immunoglobulin A dermatosis, toxic epidermal necrolysis, or exfoliative dermatitis)
- [36] have had lymphoma, leukemia, or any malignancy within the past 5 years, except for basal cell or squamous epithelial carcinomas of the skin that have been resected with no evidence of metastatic disease for 3 years
- [37] have had breast cancer within the past 10 years
- [38] have any condition that could affect pain perception from an injection
- [39] have excessive tattoos over either arm, either arm, either thigh, or either side of the abdomen that would interfere with injection-site assessments
- [40] in the opinion of the investigator, are unsuitable for inclusion in the study

### **6.2.1. Rationale for Exclusion of Certain Study Candidates**

Exclusion criteria [9] and [10] prevent conflict of interest in study subjects. Exclusion criteria [11] through [39] exclude items including, but not limited to medical conditions, medication intolerance, and concomitant medication use that may confound the assessment of study endpoints.

### **6.3. Lifestyle and/or Dietary Requirements**

Throughout the study, subjects may undergo medical assessments and review of compliance with requirements before continuing in the study. Female subjects will also be required to adhere to contraceptive requirements, as outlined in the inclusion criteria (Section [6.1](#)).

#### ***6.3.1. Meals and Dietary Restrictions***

Subjects will receive a light breakfast on the morning of Day 1 but are required to fast (water is permitted) from 1 hour prior to dosing until 1-hour postdose. Standard meals will be provided at all other times while subjects are resident at the CRU, per the CRU's policy.

#### ***6.3.2. Caffeine, Alcohol, and Tobacco***

Subjects will not be allowed to consume caffeinated products during study visits and while resident at the CRU, but otherwise subjects will be allowed to maintain their regular caffeine consumption.

Alcohol consumption is not permitted while subjects are resident at the CRU and for 24 hours prior to each study visit. Alcohol intake during outpatient periods should not exceed 3 units per day for males or 2 units per day for females. In addition, subjects must abide by the CRU smoking restrictions during study visits and while resident at the CRU.

#### ***6.3.3. Activity***

Subjects will be advised to maintain their regular levels of physical activity/exercise; however, they should not undertake vigorous or prolonged exercise within 48 hours prior to any visit in which laboratory safety tests will occur (Day -1, Day 15, Day 29, and Day 85). While certain study procedures are in progress at the site, subjects may be required to remain recumbent or sitting.

### **6.4. Screen Failures**

Individuals who do not meet the criteria for participation in this study (screen failure) may not be re-screened, except as described in exclusion criterion Section [6.2](#) [20d].

## 7. Treatment

### 7.1. Treatment Administered

One 200-mg dose of IP will consist of  $2 \times 1\text{-mL}$  SC injections using 2 PFS of 100 mg mirikizumab into the arms, thighs, or abdomen, according to the randomization schedule.

Subjects randomized to a group with the arm or thigh as the injection area will have

1. the first injection administered to the left limb, and
2. the second injection administered to the corresponding (contra-lateral) right limb.

Subjects randomized to the group with the abdomen as the injection area will have

1. the first injection administered to the lower left quadrant, and
2. the second injection administered to the lower right quadrant of the abdomen.

The second injection should be administered 20 ( $\pm 2$ ) minutes after the first injection.

This study will compare single doses of 2 formulations:

- 200 mg of Mirikizumab Reference Formulation (100 mg/mL),  $2 \times 1\text{-mL}$  PFS (administered in completed and ongoing clinical studies [see Section 3.2])
- 200 mg of Mirikizumab Test Formulation (100 mg/mL),  $2 \times 1\text{-mL}$  PFS

Trained site staff will administer all doses. Prior to the PFS injections, the investigator or designee will clean the subject's skin. The injections will be administered according to the instructions provided by the sponsor.

The investigator or designee is responsible for

- explaining the correct use of the IP to the site staff
- verifying that instructions are followed properly
- maintaining accurate records of IP dispensing and collection, and
- returning all unused medications to Lilly or its designee at the end of the study

**Note:** In some cases, site may destroy the material if, during the investigational-site selection, the evaluator has verified and documented that the site has appropriate facilities and written procedures to dispose of clinical materials.

#### 7.1.1. Packaging and Labeling

Mirikizumab will be supplied by the sponsor or its designee in accordance with current good manufacturing practice, labeled according to the country's regulatory requirements, and supplied with lot numbers, expiry dates, and certificates of analysis, as applicable.

Each 1-mL syringe of mirikizumab (100 mg/mL) is designed to deliver 100 mg of mirikizumab. The following products will be supplied by Lilly, with study-specific labels, for use in the study:

- Mirikizumab Reference Formulation (solution for injection) in 1-mL single-dose, pre-filled, disposable manual syringes
- Mirikizumab Test Formulation (solution for injection) in 1-mL single-dose, pre-filled, disposable manual syringes

### **7.1.2. *Medical Device***

The investigator or designee will ensure that the instructions have been followed properly, maintaining accurate records of study devices, dispensing, and collection. The used or unused PFS may be destroyed by a qualified vendor. However, a used PFS that is associated with a product complaint will need to be returned to Lilly.

## **7.2. *Method of Treatment Assignment***

Subjects will be randomly assigned to 1 of 2 possible treatments and 1 of 3 possible injection sites (arms, thighs, or abdomen) using a computer-generated allocation code (Section 5.1).

### **7.2.1. *Selection and Timing of Doses***

Each subject will be administered 2 injections approximately 20 minutes apart to complete the single dose. The actual time of all injections will be recorded in the subject's electronic case report form (eCRF).

## **7.3. *Blinding***

Blinding will be in place for subjects and for site staff conducting any injection-site assessments.

In case of an emergency, the investigator has the sole responsibility for determining if unblinding of a subject's treatment assignment is warranted for medical management of the event. The subject's safety must always be the first consideration in making such a determination. If the investigator decides that unblinding is warranted, it is the responsibility of the investigator to promptly document the decision and rationale and notify Lilly as soon as possible.

Upon completion of the study, all codes must be returned to Lilly or its designee.

## **7.4. *Dose Modification***

Dose modification is not permitted in this study.

### **7.4.1. *Special Treatment Considerations***

All biological agents carry the risk of systemic allergic/hypersensitivity reactions. Clinical manifestations of these reactions may include, but are not limited to, rash, pruritus (itching), urticaria (hives), angioedema (swelling of the lips and/or tongue), and anaphylactic reaction. Sometimes these reactions can be life-threatening. Proteins may also cause redness, itching, swelling, or pain locally at the injection site. Therefore, all subjects should be

- closely monitored for signs or symptoms that could result from such reactions
- educated on the signs or symptoms of these types of reactions, and

- instructed to contact the study site immediately if they experience any of these symptoms after discharge from the CRU.

If a subject experiences an acute allergic/hypersensitivity reaction after an injection of IP, he or she should be managed appropriately and receive relevant supportive care. The event should be recorded as an AE and a hypersensitivity cytokine panel ([Appendix 6](#)) should be collected.

## **7.5. Preparation/Handling/Storage/Accountability**

Investigational products will be stored under refrigerated conditions at 2°C to 8°C (36°F to 46°F) in its original carton to protect from light. Investigational products should not be frozen or shaken.

Site will be required to monitor the temperature of on-site IP storage conditions. The investigator or designee must confirm that appropriate temperature conditions have been maintained, as communicated by the sponsor, during transit for all IPs received and must confirm that any discrepancies are reported and resolved before use of the IPs.

Unblinded site staff will be responsible for handling and administering IP. Unblinded site staff are also responsible for ensuring that subjects remain blinded to treatment (ie, subjects must not see the syringe before, during, or after IP administration). Blinded assessors of any injection-site assessments and bleeding will not have access to the IP.

Only subjects enrolled in the study may receive IPs or study materials, and only authorized site staff may supply or administer IPs. All IPs should be stored in an environmentally controlled and monitored (manual or automated) area in accordance with the labeled storage conditions with access limited to the investigator and authorized site staff.

The investigator is responsible for IP accountability, reconciliation, and record maintenance (such as receipt, reconciliation, and final disposition records).

## **7.6. Treatment Compliance**

The IPs will be administered at the clinical site, and documentation of treatment administration will occur at the site.

## **7.7. Concomitant Therapy**

Subjects on stable concomitant medication at the time of study entry should continue their regular, unchanged dose throughout the study. Permitted concomitant medications, at the discretion of the investigator, include hormonal contraceptives, hormone replacement therapy, and thyroid replacement. In addition, occasional acetaminophen is acceptable at the discretion of the investigator. However, acetaminophen should not be administered on the dosing day within 4 hours prior to the first injection and until at least 4 hours after the second injection. No more than 3 g of acetaminophen will be permitted in any 24-hour period. Inclusion of subjects on any other concomitant medication (eg, statins and anti-hypertensives) is contingent upon approval following consultation with the sponsor.

Subjects will be restricted from applying any creams or lotions on the arm, thigh, or abdominal skin within 24 hours prior to and after the injection and subjects should not receive any additional SC injections at the site of mirikizumab administration for the duration of the study.

If the need for any additional concomitant medication arises, inclusion or continuation of the participant may be at the discretion of the investigator after consultation with a Lilly clinical pharmacologist (CP) or clinical research physician (CRP). Any medication used during the study must be documented.

## **7.8. Treatment after the End of the Study**

This section is not applicable for this study.

## 8. Discontinuation Criteria

Subjects discontinuing from the study prematurely for any reason should complete AE and other Day 85/early discontinuation procedures per Section 2 of this protocol.

### 8.1. Discontinuation from Study Treatment

Not applicable in this single-dose study.

#### 8.1.1. Discontinuation of Inadvertently Enrolled Subjects

If the sponsor or investigator identifies a subject who did not meet enrollment criteria and was inadvertently enrolled, a discussion must occur between the Lilly CP/CRP and the investigator to determine if the subject may continue in the study. If both agree it is medically appropriate to continue, the investigator must obtain documented approval from the Lilly CP/CRP to allow the inadvertently enrolled subject to continue in the study. If the subject received IP, he or she will continue to be monitored for safety and tolerability for the planned duration of the study.

### 8.2. Discontinuation from the Study

Subjects will be discontinued under the following circumstances:

- Enrollment in any other clinical study involving an IP or enrollment in any other type of medical research judged not to be scientifically or medically compatible with this study prior to receiving IP in this study. If the subject received IP, he or she will continue to be monitored for safety and tolerability for the planned duration of the study.
- Participation in the study needs to be stopped for medical, safety, regulatory, or other reasons consistent with applicable laws, regulations, and good clinical practice (GCP).
- Investigator decision
  - the investigator decides that the subject should be discontinued from the study
- Subject decision
  - the subject, or legal representative, requests to be withdrawn from the study

### 8.3. Subjects Lost to Follow-up

A subject will be considered lost to follow-up if he or she repeatedly fails to return for scheduled visits and is unable to be contacted by the study site. Site staff are expected to make diligent attempts to contact subjects who fail to return for a scheduled visit or were otherwise unable to be followed up by the site.

## 9. Study Assessments and Procedures

Section 2 lists the Schedule of Activities, detailing the study procedures and their timing (including tolerance limits for timing).

Appendix 2 lists the laboratory tests that will be performed for this study.

Appendix 5 provides a summary of the maximum number and volume of invasive samples, for all sampling, during the study.

Unless otherwise stated in subsections below, all samples collected for specified laboratory tests will be destroyed within 60 days of receipt of confirmed test results. Certain samples may be retained for a longer period, if necessary, to comply with applicable laws, regulations, or laboratory certification standards.

### 9.1. Efficacy Assessments

This section is not applicable for this study.

### 9.2. Adverse Events

Investigators are responsible for monitoring the safety of subjects who have entered this study and for alerting Lilly or its designee to any event that seems unusual, even if this event may be considered an unanticipated benefit to the subject.

The investigator is responsible for the appropriate medical care of subjects during the study.

Investigators must document their review of each laboratory safety report.

The investigator remains responsible for following, through an appropriate health care option, AEs that are serious or otherwise medically important, considered related to the IP or the study, or that caused the subject to discontinue the IP before completing the study. The subject should be followed up until the event resolves, stabilizes with appropriate diagnostic evaluation, or is reasonably explained. The frequency of follow-up evaluations of the AE is left to the discretion of the investigator.

The investigator will record all relevant AE and SAE information in the eCRF. After the informed consent form is signed, site staff will record, via eCRF, the occurrence and nature of each subject's preexisting conditions. Additionally, site staff will record any change in the condition(s) and the occurrence and nature of any AEs.

The investigator will interpret and document whether or not an AE has a reasonable possibility of being related to study treatment, study device, or a study procedure, taking into account the disease, concomitant treatment, or pathologies.

A "reasonable possibility" means that there is a potential cause and effect relationship between the IP, study device and/or study procedure, and the AE.

Planned surgeries should not be reported as AEs, unless the underlying medical condition has worsened during the course of the study.

Prospective collection of ISRs at predefined time points is included as part of this protocol. As such, any identified ISRs will not be collected as AEs but will instead be recorded using the predefined ISR collection tools.

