Single 12-lead ECG (supine)	X															X	Single screening ECG but may be obtained at additional times, when deemed clinically necessary.	

Procedure	Screening	Study Day																Comments
		-1	1	3	5 ±1d	8 ±1d	11 ±1d	15 ±2d	22 ±2d	29 ±2d	36 ±2d	43 ±2d	50 ±2d	57 ±3d	64 ±2d	71 ±3d	85 ±3d or ED	
Mirikizumab administration (2 injections per dose)	-28 to -2 days prior to Day 1			X														See Section 7.1. Subjects will fast (only water is allowed) from 1 hour before until 1 hour after dosing. Injections at Times 0 and 20 ± 2 min.
CCI				1														Assess within the first minute and then, if there is bleeding, at 1-min intervals following the injection until the bleeding stops. See Section 9.4.5.2.
CCI				1, 5, 15, 30, 60, 120, 240													Assess all injections as described in Section 9.4.5.3. Time points on Day 1 after each injection are 
 
• within 1 min,
 
• 5 min (±1.5 min)
 
• 15 and 30 min (each ±2 min), and
 
• 60, 120, and 240 min (each ±5 min).
 
• For VAS, see Section 9.4.5.3.1.
 
	
Mirikizumab PK sample			P	X	X	X	X	X	X	X	X	X	X	X	X	X		

Procedure	Screening -28 to -2 days prior to Day 1	Study Day																Comments
		-1	1	3	5 ±1d	8 ±1d	11 ±1d	15 ±2d	22 ±2d	29 ±2d	36 ±2d	43 ±2d	50 ±2d	57 ±3d	64 ±2d	71 ±3d	85 ±3d or ED	
CC1 F			P					X		X							X	
CC1 F		X																
AE and concomitant medication		X	X	X	X	X	X	X	X	X	X	X	X	X	X	X	ISRs will be reported on supplemental ISR form, and not as AEs	

Abbreviations: AE = adverse event; BMI = body mass index; CRU = clinical research unit; d = day; ECG = electrocardiogram; ED = early discontinuation;

FSH = follicle-stimulating hormone; ISR = injection-site reaction; min = minutes; P = pre-dose; PK = pharmacokinetic(s); SC = subcutaneous; TB = tuberculosis; VAS = visual analog scale.

a Administration of the pain VAS is mandatory at 1, 5, and 15 min regardless of whether pain is reported as "yes" or "no" during the injection-site assessment. At other time points, the VAS is administered only if pain is reported as "yes" during an injection-site assessment.

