### **9.2.1. Serious Adverse Events**

An SAE is any AE from this study that results in 1 of the following:

- death
- initial or prolonged inpatient hospitalization
- a life-threatening experience (ie, immediate risk of dying)
- persistent or significant disability/incapacity
- congenital anomaly/birth defect
- important medical events that may not be immediately life threatening or result in death or hospitalization but may jeopardize the subject or may require intervention to prevent 1 of the other outcomes listed in the definition above

Site staff must alert the Lilly CRP/CP, or its designee, of any SAE as soon as practically possible.

Additionally, site staff must alert Lilly Global Patient Safety, or its designee, of any SAE within 24 hours of investigator awareness of the event via a sponsor-approved method. If alerts are issued via telephone, they are to be immediately followed up with official notification on study-specific SAE forms. This 24-hour notification requirement refers to the initial SAE information and all follow-up SAE information.

Although all AEs are recorded in the eCRF after signing informed consent, SAE reporting to the sponsor begins after the subject has signed informed consent and has received IP. However, if an SAE occurs after signing informed consent, but prior to receiving IP, AND is considered Reasonably Possibly Related to a study procedure then it MUST be reported.

Investigators are not obligated to actively seek AEs or SAEs in subjects once they have discontinued from and/or completed the study (the subject summary eCRF has been completed). However, if the investigator learns of any SAE, including a death, at any time after a subject has been discharged from the study, and he/she considers the event reasonably possibly related to the study treatment or study participation, the investigator must promptly notify Lilly.

Pregnancy (maternal or paternal exposure to IP) does not meet the definition of an AE. However, to fulfill regulatory requirements any pregnancy should be reported following the SAE process to collect data on the outcome for both mother and fetus.

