**Appendix 1. Abbreviations and Definitions**

---

Term	Definition
ADA	antidrug antibody
AE	adverse event: Any untoward medical occurrence in a patient or clinical investigation subject administered a pharmaceutical product that does not necessarily have a causal relationship with this treatment. An AE can therefore be any unfavorable and unintended sign (including an abnormal laboratory finding), symptom, or disease temporally associated with the use of a medicinal (investigational) product, whether or not related to the medicinal (investigational) product.
ALP	alkaline phosphatase
ALT	alanine aminotransferase
AUC	area under the concentration versus time curve
AUC(0-∞)	area under the concentration versus time curve from time zero to infinity
AUC(0-tlast)	area under the concentration versus time curve from time zero to time t, where t is last the time point with a measurable concentration
blinding	A procedure in which 1 or more parties to the study are kept unaware of the treatment assignments. Unless otherwise specified, blinding will remain in effect until final database lock.  A single-blind study is one in which the investigator and/or site staff are aware of the treatment, but the subject is not, or vice versa; or when the sponsor is aware of the treatment, but the investigator, site staff, and the subject are not. A double-blind study is one in which neither the subject nor any of the investigator or sponsor staff who are involved in the treatment or clinical evaluation of the subjects are aware of the treatment received.
BMI	body mass index
CI	confidence interval
Cmax	maximum observed drug concentration
complaint	A complaint is any written, electronic, or oral communication that alleges deficiencies related to the identity, quality, purity, durability, reliability, safety or effectiveness, or performance of a drug or drug delivery system.
compliance	Adherence to all the study-related requirements, good clinical practice (GCP) requirements, and the applicable regulatory requirements.

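### Could a serious injection-site reaction drop out of serious adverse event reporting because these reactions are kept off the adverse event form?

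*Protocol*

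**What the plan says.** Protocol section 9.2 explains that "Prospective collection of ISRs at predefined time points is included as part of this protocol" and concludes that "any identified ISRs will not be collected as AEs but will instead be recorded using the predefined ISR collection tools". In the Schedule of Activities, the comment on the row for AEs and concomitant medication says the same: "ISRs will be reported on supplemental ISR form, and not as AEs". Neither place makes an exception for serious events.

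Section 9.2.1 opens its definition with "An SAE is any AE from this study that results in 1 of the following" and then lists the seriousness criteria. It requires notification of the sponsor's safety group within 24 hours of the investigator becoming aware of an SAE. Appendix 1 defines an AE as "Any untoward medical occurrence in a patient or clinical investigation subject administered a pharmaceutical product", whether or not the product caused it.

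Three outputs depend on the classification. TEAEs and SAEs are the endpoint for the secondary objective (Protocol section 4). The number of SAEs related to the product is to be reported (Protocol 10.3.1.1). SAEs are to be listed (SAP 9.4.1).

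**The concern.** Read literally, the two rules can be chained: ISRs are not collected as AEs, only an AE can be an SAE, so a serious local ISR is never an SAE. It would then sit on the ISR form, outside the SAE listing and outside 24-hour notification. That would matter here because the test formulation is being given to people for the first time (Protocol 3.1) and was developed to lessen these reactions.

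The rule also looks wider than its reason. It is justified by scheduled collection, and the visible schedule for injection-site checks is short: "Time points on Day 1 after each injection are" introduces a list whose last timed entry is "60, 120, and 240 min (each ±5 min". The rule nevertheless covers every identified ISR, and the comment stating it belongs to a row that runs to Day 85.

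**Working it through.** The plan gives no figure to reproduce. The question is how four pieces of text fit together.

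1. **What the ISR rule does.** Section 9.2 concerns collection and names a different instrument for it. It does not say that an ISR is not an AE. The Schedule comment is also about which form is used.

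2. **Whether an ISR is still an AE.** The Appendix 1 definition is broad and has no carve-out for ISRs, so a local reaction after dosing meets it.

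3. **Whether a serious ISR is an SAE.** Section 9.2.1 applies to any AE that meets a listed criterion. From step 2, a serious ISR qualifies. The notification duty depends on seriousness and on the investigator's awareness, not on which form holds the event.

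4. **Comparison with pregnancy.** Where the protocol takes something out of AE status, it says so. Section 9.2.1 states that pregnancy is not an AE and therefore has to route it expressly through the SAE process. An ISR is not declared a non-AE, so it needs no such route.

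5. **What is left uncovered if steps 1 to 3 are rejected.** Acute allergic or hypersensitivity reactions are recorded as AEs (Protocol 7.4.1). Infections and systemic hypersensitivity are AEs of special interest (9.2.1.2). What remains is a serious local reaction that is neither allergic nor infectious. For that, section 9.2 still makes investigators responsible for "alerting Lilly or its designee to any event that seems unusual", and the sponsor monitors safety data throughout (9.4.6). SAP 9.1 promises listings of all data in the database, so an event held only on the ISR form would still be listed, assuming that the form is databased.

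6. **How likely that is.** The documents give no rate of serious ISRs, so none is estimated. Section 3.2.1 reports no SAEs in the Phase 1 studies. Section 3.2 describes ISRs in the earlier formulation studies as varying in frequency but mostly of low grade.

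Two simple calculations suggest themselves, but neither decides the point.

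- **Time window.** The visible injection-site time points cover 240 minutes of the 84 days from Day 1 to Day 85: 240 / (84 × 1,440) = 240 / 120,960 = 0.2%. This describes scheduled checks. It does not bear on how a serious event is classified, and under the Schedule comment a later ISR still goes on the form.
- **Arm-level proportion.** One event is 1/24 = 4.2% of the planned completers in an arm, or 1/30 = 3.3% if all 60 subjects enrol and split equally. This is only one over the arm size for a hypothetical event. The visible plan specifies a listing of SAEs and a count of related ones, not an SAE percentage by arm. The safety population in SAP section 8 is all dosed subjects, not completers.

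**The case for a change.** The best case for a change is that no visible sentence says what happens to a serious ISR, and site staff follow forms more readily than definitions. The Schedule comment is blunt enough that someone could apply it literally. The protocol does qualify exclusions elsewhere: the planned-surgery exclusion in section 9.2 has its own limiting clause. The duty to alert the sponsor to unusual events is tied neither to seriousness nor to the 24-hour limit. The adverse device effect rules do not help, because they too are defined through AEs. A single sentence would cost almost nothing.

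Much of this is fair. The two readings do exist, and a cross-reference from section 9.2 to the SAE process would be tidy. But the readings are not equally supported. The form-only reading has to turn a recording instruction into a reclassification that the text never states. The planned-surgery clause limits an exclusion from reporting, whereas the ISR rule moves the record to another instrument. Most importantly, the collection tools named in section 9.2 belong to Protocol 9.4.5.3, with analysis in SAP 9.4.9 and 9.4.10, and all three are redacted. The sentence being asked for may already be there.

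**Conclusion.** No change to the plan is called for. The visible text leaves a detail unstated, and investigators and analysts would ordinarily fill it correctly: an ISR that meets a seriousness criterion is an AE under Appendix 1, hence an SAE under section 9.2.1, wherever else it is also recorded. No rule that gives a wrong result has been shown.

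The consequence is small. If a site took the other reading and such an event occurred, one entry would be missing from the SAE listing and, if the event was judged related, the related-SAE count would be one too low. It would also miss the 24-hour route unless another safeguard caught it. $C_{max}$ and both AUC endpoints, their model and the sample size do not depend on the point.

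This rests on two assumptions: that sites apply the protocol's own AE definition when judging seriousness, and that the redacted injection-site sections do not say the opposite. Anyone holding the unredacted documents can check the second directly.
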